We aim to understand which messaging strategies are most successful at communicating information about Covid-19 to underserved communities. The goal is to understand how to best structure messaging to make them more impactful. We are measuring "impact" as a) trust in information coming from the healthcare system; b) attention and retention of key facts about Covid-19 presented in the videos; c) interest in following the advice in the videos pertaining to social distancing, hygiene and mask-wearing;

¹See Appendix Section A for transcripts of the videos.

and d) health-seeking behavior.

We hypothesize that overall videos delivered by concordant messengers will be more effective. Moreover, acknowledging the “elephant in the room” –i.e., explicit acknowledgment of inequalities – will make the videos more impactful, especially for discordant doctor messengers. We also hypothesize that videos delivered by our partner doctors (even of discordant race or ethnicity) will be more impactful than one delivered by a representative of the CDC. Finally, for individuals who believe that mask wearers are likely to be viewed as sick or up to no good by larger than what we are informing them, we predict that presenting information about beliefs will increase demand for mask wearing.

2. Treatments, and Experimental Protocols

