4.2 Data quality checks

We have several questions in the survey that capture respondent attention. We will check that low quality survey responses are not affected by the treatments. If they are not, we will exclude low quality survey responses. We also plan to exclude those that take very little time on the survey overall and/or on the videos.

5. Empirical Analysis

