5.2 Key Outcomes

We intend to measure the treatment effects on the following families of outcomes. Outcomes marked (T) pertain to trust in the medical system or in health information. Outcomes marked (SD-H) pertain to the social distancing and hygiene content from the CDC video. Outcomes marked (M) pertain to mask-wearing.

1. Attention and Assessments (T):
 - (a) Ratings and trust, willingness to share videos as described above,
 - (b) Time spent watching the videos
2. Knowledge of information presented in the video (retention)
 - (a) Basic information about symptoms
 - (b) Information covered in the CDC video (SD-H)
 - (c) Information covered in the mask video (M)
3. Measures related to trust in the health-care system and health-seeking behavior (T).
4. Views on Mask-wearing (M)
5. Interest in more information about masks and allocations to organizations supporting mask-wearing (M)
6. Interest in more information pertaining to social distancing and hygiene (SD-H)

We will construct indices for each family, where applicable. We will also adjust our inferences for multiple outcome testing.

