5.3 Regression Analysis

We will do two types of analysis: identifying effective videos in our sample, and general tests of the hypotheses described above.

- Best treatment

We are interested in selecting the best combination of types of video for scale up. In order to identify the most effective combination of videos, we will adapt a disciplined pooling methods of Banerjee et al (2020) for selecting the most effective combination of treatments (to a settings were we have large

sample within each of 16 treatment cells), and Andrews et al (2020) to correct for small sample bias in estimating the impact the most effective method.⁶

For this specific question of whether *our* messages of a given type (concordant race, correcting priors, etc), since random assignment is done by individuals, we do not adjust standard errors. This is the correct analysis for scaling up these videos per-se.

- Hypothesis tests

In order to test the hypotheses listed above, we run the following contrasts (Hispanic and Black will be run separately for all the contrasts:

Main hypotheses tests:

1. Is there any impact of the videos (treatment vs control)
2. Concordant vs. discordant messengers: pooled across all
3. [name] with "no elephant" and the two different versions of "elephant in the room", no [name] each compared to the "no elephant, no [name]" condition
4. [name] versus everything else.
 - For social distancing and hygiene (largest effect expected here for the [name] treatment)
 - For other outcomes
5. Mask-debiasing treatment on mask outcomes, heterogenous based on respondent prior beliefs (lower or higher than 8 out of 10 people think mask wearer is helping the community).

Secondary hypotheses tests

1. [name] treatment effects will be interacted with concordant doctor
2. [name] treatment effect will be interacted with social debiasing treatment (which may be less effective after presenting [name])
3. Elephant treatment will be interacted with concordant doctor
4. Mask treatment effect will be interacted with concordant doctor
5. Mask treatment effect will be interacted with elephant treatment
6. [name] treatment effect will be interacted with elephant treatment
7. Gender of provider will be interacted with concordant doctor and/or respondent gender

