Appendix

A. Video Scripts

A.1 Videos for African American Viewers

Full script is: Video 1A+[Video 1B or Video 1C or Video 1D] + Video 1E + Video 2 + Video 3A+ [Nothing or Video 3B] + Video 3C

Video 1A:

[start with mask, remove it] Hello, I?m Dr [YOUR LAST NAME HERE] from [YOUR INSTITUTIONAL AFFILIATION HERE], and I?d like to tell you a little about Coronavirus or COVID-19. COVID-19 is a new virus that can infect the respiratory tract and lungs. Although many people who get sick from COVID will get better, some people who get it become very ill and some even die.

Video 1B:

Although there?s no cure, there are ways medical professionals have found to protect you and your community from COVID. I hope that this message can give you information that will help you protect you or someone you love from COVID infection.

Video 1C:

Even though everyone is affected, communities of color have been especially hit hard by the COVID 19 epidemic. Although there is no cure there are ways medical professionals have found to protect you and your community from COVID. Now, I know the medical system has not always earned your trust and still remains unequal in how it treats individuals today. But I hope that this message can give you information that will help protect you or someone you love from COVID infection.

Video 1D:

Even though everyone is affected, communities of color have been especially hard hit by the COVID 19 epidemic, due to a long history of inequality. Many of the jobs done by minorities are essential and cannot be done remotely, which increases the risk of getting the virus. Additionally, when one lives in tight spaces, it is also much more difficult to keep a safe distance. But I hope that this message can give you information that will help you protect you or someone you love from COVID infection.

Video 1E:

First, I would like to tell you about the symptoms of COVID-19. The most common symptoms of COVID-19 are cough, fever, and trouble breathing. Another odd symptom some people have is loss of taste or smell. A large number of people who have COVID-19 actually don?t show any symptoms at all. Unfortunately, people can still spread the disease to others even with no symptoms. The next video will provide you with more information on how you can protect yourself and others.

Video 2:

[start with mask, remove it]

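### Viewing time is an attention outcome with no adjustment for clip length, yet by script Video 1 is 21% to 37% longer in the elephant arms than in base

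*Combined protocol and SAP*

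**What the plan says.** The Introduction counts "attention and retention of key facts about Covid-19 presented in the videos" as one component of impact, and predicts that acknowledging inequalities will raise impact. Section 5.2 puts "Time spent watching the videos" in family 1, beside the video ratings. It gives no unit, no split by video and no adjustment for length. It adds: "We will construct indices for each family, where applicable".

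In Section 5.3, main test 3 compares each elephant version with the condition that has no elephant text and a partner doctor in Video 2, separately for Black and Hispanic respondents. Main test 4 sets the CDC clip "versus everything else", first for social distancing and hygiene outcomes and then for the others.

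Appendix A builds the first video, in both groups, as "Video 1A+[Video 1B or Video 1C or Video 1D] + Video 1E". The elephant text (1C or 1D) replaces the base insert 1B, and the rest is common. For example, the African American 1C opens with "Even though everyone is affected, communities of color have been especially hit hard by the COVID 19 epidemic", a sentence that 1B lacks. In Figure 1, cells 1/3/4 (no mask debiasing) and 5/7/8 (debiasing) are base, Elephant 1 and Elephant 2; cells 2 and 6 carry the CDC clip.

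**The concern.** Clip length is part of the assigned treatment. If time is recorded in seconds, a person equally willing to finish either version logs more time in the elephant arm simply because there is more to watch. Randomization, strata controls and Lasso-selected covariates cannot remove this. Standard errors that allow for a doctor-video effect widen the interval but leave the estimate where it is. The later rating survey considered in Section 6.1 covers production and speaker traits on common portions, not length.

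At stake is one named attention outcome in a main hypothesis test, with a bias towards the study's own prediction, and the family 1 index if time enters it. Ratings, knowledge, trust and mask outcomes are not touched. Selection of videos for scale-up is affected only if it uses viewing time or that index, which the plan does not say.

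**Working it through.** The plan states no running time, SD of viewing time or power, so there is no figure of its own to reproduce.

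**1. Script lengths.** Whitespace-separated words in the English scripts of Appendix A, stage directions left out, each name or affiliation placeholder counted as one word:

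| Group | 1A | 1B | 1C | 1D | 1E |
|---|---|---|---|---|---|
| African American | 54 | 41 | 82 | 88 | 81 |
| Hispanic | 55 | 41 | 106 | 79 | 81 |

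**2. Video 1 = 1A + insert + 1E.**

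| Group | Base | Elephant 1 | Elephant 2 |
|---|---|---|---|
| African American | 176 | 217 (+23.3%) | 223 (+26.7%) |
| Hispanic | 177 | 242 (+36.7%) | 215 (+21.5%) |

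Other ways of handling placeholders, hyphens or characters move the extremes only to 19.6% and 37.7%.

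**3. Seconds.** Extra words are 41, 47, 65 and 38. At an assumed 150 words per minute (words / 150 × 60) this is 16.4, 18.8, 26.0 and 15.2 s. Over 170 to 130 words per minute the range is 13 to 30 s.

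**4. Summed over three videos.** With a partner doctor in Video 2 (125 words) and no debiasing in Video 3 (53 + 65 words), the base totals are 419 and 420 words. The increases are 41/419 = 9.8%, 47/419 = 11.2%, 65/420 = 15.5% and 38/420 = 9.0%. Where 3B is added (82 or 74 words) they fall to about 8% to 13%.

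**5. Who contributes.** Someone who finishes the longer clip adds the full extra time; someone who stops at a fixed second before the base clip ends adds none. If a share p would finish the longer clip, the mean shift is at least p × the extra seconds: 9 to 16 s at p = 60% (0.6 × 15.2; 0.6 × 26.0) and 14 to 23 s at p = 90%. Both values of p are assumptions.

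**6. Against the trial's precision.** Assume 17 equal groups (16 cells plus control; the plan states no allocation). With 10,000 Black and 5,000 Hispanic respondents that is about 588 and 294 per cell. Each side of an elephant comparison has four cells, about 2,353 and 1,176 people. The difference detectable with 80% power at two-sided 5%, from 2.80 × √(2/n), is about 0.08 and 0.12 SD. If the SD were 60 s, the full shift would be 15.2/60 = 0.25 to 26.0/60 = 0.43 SD, and 9 s would be 0.15 SD. If it were 120 s, 9 s would be 0.08 SD, below what the Hispanic comparison could reliably detect.

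**7. Index.** With k equally weighted standardized items, an assumed correlation of 0.3, and a shift of d SD in one item, the index shift is (d/k) / √((1 + 0.3(k − 1))/k). Section 2.3 has four ratings after each of three videos, so 12 ratings plus time gives k = 13. At SD 60 s the shift is 0.03 to 0.06 SD, with false positives of 11% to 28% at nominal 5%; at SD 120 s, 7% to 11%. With only four ratings plus time (k = 5), the rates are 40% to 90% and 14% to 37%. All of these give every viewer the full extra time, assume independent respondents, and precede the planned multiplicity adjustment.

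**8. Main test 4.** In Figure 1 the CDC-clip cells have no elephant text. If the comparator is the other treated cells in equal numbers, its Video 1 is longer by (0 + 41 + 47)/3 = 29.3 or (0 + 65 + 38)/3 = 34.3 words, about 12 or 14 s at 150 words per minute. Video 1 is shown before the CDC clip, so this gap cannot be caused by it.

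**The case against.** The strongest reply is that the plan leaves the unit open and the sponsor may intend a scaled measure; one sentence saying so would settle the raw-seconds problem. That is fair, but the outcome as written is time, and nothing elsewhere supplies a scale.

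The outcome also refers to the videos in the plural, so the summed figure of about 9% to 16% may be the relevant one. That stands, and both figures belong in the point. Recorded durations and Spanish scripts are not in the documents, so the percentages rest on English word counts and equal pace.

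Four stronger readings are tempting but not supported:

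- **A shift of 6 to 11 standard errors.** This is what SD 60 s and the full extra time for everyone would give. But the base Video 1 lasts about 70 s (176/150 × 60), and time bounded between 0 and 70 s cannot have an SD above 35 s. An SD of 60 s or more implies pauses, replays or idle page time, and with a smaller SD much of the spread comes from early leavers, who add little.
- **A false-positive rate of 40% to 90% in the index.** This needs only four ratings in the index, whereas Section 2.3 collects 12, and the plan does not say that time enters it.
- **Main test 4 showing the CDC clip losing attention.** On summed time the sign is unknown, because the clip's length is not given. The plan tests shut-down through attitudes to masks. Secondary test 6 crosses the CDC speaker with elephant text, which Figure 1 does not show.
- **Arm-dependent exclusions.** Section 4.2 says "We also plan to exclude those that take very little time on the survey overall and/or on the videos" but states no cut-off, and a low floor would hardly depend on a 70 s versus an 85 to 97 s clip.

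**Conclusion.** The concern holds as a matter of outcome definition. Taken in seconds, 1(b) favours the elephant arms in main test 3 for anyone who watches to the end, without any gain in attention. By script the excess is 21% to 37% of Video 1, or about 9% to 16% of all three videos without debiasing. The seconds (15 to 26) depend on an assumed 150 words per minute and on how many people finish. The effect on a family 1 index cannot be fixed from the plan. It is small to moderate if all 12 ratings are included, and larger only if the index is short. For main test 4 the supportable claim is narrow: Video 1 time should not count there, because it precedes the CDC clip and differs by script. This is worth correcting before analysis, but it does not threaten the trial's other outcomes.

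**What to change.** - For the elephant comparisons in main test 3, define 1(b) as time on Videos 2 and 3 only, and use that in any family 1 index. Their scripts are identical in cells 1/3/4 and in cells 5/7/8.
- Report Video 1 as the share of the assigned clip watched, beside its running time, as description. Share watched is neutral if both arms watch the same fraction. If viewers leave at a constant rate per second, the longer clip shows a lower share, so it should not carry the test.
- For main test 4, leave out Video 1 time and raw Video 2 time. Use Video 3 time if viewing time is analysed there.

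The cost is an outcome definition; no new arm or recording is needed. It requires time logged for each video, which the plan does not state but which its time outcome and exclusion rule suggest. There are two drawbacks. Time no longer tests attention within Video 1, where a direct reaction to the elephant text would show first. And people who leave during Video 1 need a stated rule, either zero time on the later videos or attrition.

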5.3 Regression Analysis

We will do two types of analysis: identifying effective videos in our sample, and general tests of the hypotheses described above.

- Best treatment

We are interested in selecting the best combination of types of video for scale up. In order to identify the most effective combination of videos, we will adapt a disciplined pooling methods of Banerjee et al (2020) for selecting the most effective combination of treatments (to a settings were we have large

sample within each of 16 treatment cells), and Andrews et al (2020) to correct for small sample bias in estimating the impact the most effective method.⁶

For this specific question of whether *our* messages of a given type (concordant race, correcting priors, etc), since random assignment is done by individuals, we do not adjust standard errors. This is the correct analysis for scaling up these videos per-se.

- Hypothesis tests

In order to test the hypotheses listed above, we run the following contrasts (Hispanic and Black will be run separately for all the contrasts:

Main hypotheses tests:

1. Is there any impact of the videos (treatment vs control)
2. Concordant vs. discordant messengers: pooled across all
3. [name] with "no elephant" and the two different versions of "elephant in the room", no [name] each compared to the "no elephant, no [name]" condition
4. [name] versus everything else.
 - For social distancing and hygiene (largest effect expected here for the [name] treatment)
 - For other outcomes
5. Mask-debiasing treatment on mask outcomes, heterogenous based on respondent prior beliefs (lower or higher than 8 out of 10 people think mask wearer is helping the community).

Secondary hypotheses tests

1. [name] treatment effects will be interacted with concordant doctor
2. [name] treatment effect will be interacted with social debiasing treatment (which may be less effective after presenting [name])
3. Elephant treatment will be interacted with concordant doctor
4. Mask treatment effect will be interacted with concordant doctor
5. Mask treatment effect will be interacted with elephant treatment
6. [name] treatment effect will be interacted with elephant treatment
7. Gender of provider will be interacted with concordant doctor and/or respondent gender

Everywhere, we will control for the strata, race/ethnicity, and where applicable, choice of English versus Spanish. Robustness of results to any possible chance unbalance will be checked by running the Belloni et al. Lasso procedure to select control variables.

⁶Banerjee, Abhijit, Arun Chandrasekhar, Esther Duflo, Matthew O. Jackson, John Floretta, Harini Kannan, Francine Loza, Anirudh Sankar, and Anna Schrimpf (2020) "Selecting the most effective nudge: evidence from a large scale experiment on immunization," Working Paper.)

For this more general analysis of whether a given type of video is more effective in general, one may want to consider a hypothetical where the videos we use were drawn from a larger pool of possible videos (i.e. we recruited N doctors but could have recruited $2N$ doctors from the same pool). In this broader exercise, one also wants to adjust standard errors to account for the possible doctor-video random effect. We will develop and implement the correct methods to do so.

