2.1 Treatments

Each subject watches three videos. Each video features a different doctor. All partner doctors viewed in the videos by a given subject are of the same racial or ethnic background.²

1. Video 1:

- Introduction
- Discussion of symptoms
- Acknowledgement of “elephant in the room” issues, where applicable.

2. Video 2:

- Information about social distancing and hygiene

3. Video 3:

- Information about masks

We are varying four aspects of the videos across treatments:

1. Racial or ethnic concordance with partner doctors in the videos (note that we side-step the issue of language: for Spanish speakers, they can chose English or Spanish, and there are non ethnically Hispanic doctors speaking in Spanish).³
2. Video 1 content: Elephant in the room
 - No elephant in the room content
 - Elephant in the room 1: Trust or Fear
 - Elephant in the room 2: Economic Inequality

²However, some individuals may see two black doctors and [name] from the CDC, a white doctor and representative of the US government.

³However we do not have recordings in other languages.

3. Identity of the doctor delivering Video 2

- Pre-recorded video of [name] of the CDC in front of the White House
- Partner doctor

4. Video 3 content: mask debiasing

- Basic mask information, no perceptions information
- Basic mask information, perceptions information
 - For the latinx community, the video discusses perceptions that the mask-wearer is sick.
 - For the black community, the video discusses perceptions that the mask-wearer is “up to no good.”
 - In both cases the message reports responses from a prior survey of perceptions that mask wearers in photos of the same racial/ethnic group are “protecting the community.”

All of the video scripts can be found in Appendix Section A. Figure 1 shows how these different treatments are incorporated in the randomization design.

Figure 1: Treatment Design: There are 8 content-variants for each video, shown here. Cell 1c/d includes the baseline information package. For each combination of message content, the partner doctors in the video may either be of a concordant (c) or discordant (d) racial/ethnic background.

All treatments receive basic information +	Doctor-Delivered CDC Message	[name] -Delivered CDC Message	Elephant 1: Fears (L) or Trust (A)	Elephant 2: Economic Inequality
No Mask Debiasing	1c/d	2c/d	3c/d	4c/d
Mask Debiasing	5c/d	6c/d	7c/d	8c/d

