2.3 Experimental Protocols and Treatments

Our experiment has the following structure:

1. Recruitment and Baseline survey
 - (a) Recruit target sample via Lucid
 - (b) For Hispanic respondents, elicit a preference for English or Spanish. Those with a preference for Spanish will be given Spanish language survey questions and will see treatment videos recorded in Spanish as well.⁴
 - (c) Collect demographic information and healthcare experience. Several demographics variables are being collected directly by Lucid.
2. Randomize Subjects to treatment
 - Treatment scripts are tailored to each racial/ethnic group
 - Within racial/ethnic group, treatment is stratified on age, gender and geographic region.
 - Randomization is at the individual level according to Figure 1.
 - There will also be a control group who will receive COVID-19 information at the very end of the survey.
3. Video delivery for all individuals not in the pure control group.
 - (a) After each of the three videos, respondents evaluate the video's usefulness, and trustworthiness, along with the respondents intention to follow the advice in the video and share information from the video.
 - (b) Prior to the third video (masks), individuals will answer questions about second order beliefs about mask wearers.
4. Endline survey
5. Videos shown to the pure control group.
6. Debrief script
7. Follow-up survey
 - (a) We are tentatively planning to follow up with participants several days post-treatment
 - (b) The chief purpose would be to measure health-seeking and health-preserving behaviors.⁵
8. Once we learn which messaging strategy is most effective, we will scale up that treatment more broadly (distributing it through social media etc.)

⁴The one exception is the CDC video with [name]. This is always shown in English.

⁵We do not commit on analyzing this data or even fully implementing a follow up because it is quite difficult to successfully follow up with online survey participants, so it will depend on our success in finding people in our pilot.

3. General Hypotheses to be Tested

This section lists the general hypotheses we want to test. For those, we are planning to run broadly pooled treatments (and specific interactions specified below).

Main hypotheses:

1. What is the overall effect of any combination of videos, compared to the control group?
2. Does racial concordance between the doctor messenger and recipient give the message higher impact across the board?

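### For Video 1 ratings, main test 3 leaves half of the valid no-elephant cells out of the elephant scripts' reference group, which loses some precision but causes no bias

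*Combined protocol and SAP*

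**What the plan says.** All references are to the combined protocol and SAP; the bracketed placeholder in its text stands for the CDC representative.

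- Section 5.3, main test 3, takes the CDC message without elephant content and the two elephant scripts without the CDC message, "each compared to the 'no elephant, no [name]' condition". It makes no exception by outcome.
- Section 2.1 places the elephant variation in Video 1. The CDC variation is the "Identity of the doctor delivering Video 2".
- Section 2.3, step 3(a): "After each of the three videos, respondents evaluate" it for usefulness and trustworthiness, and state whether they intend to follow the advice and share the information.
- Section 5.2, family 1, contains "Ratings and trust, willingness to share videos as described above" and time spent watching. Indices are to be built for each family where applicable.
- Section 4 places the endline module after Video 3.
- Section 5.3, secondary test 3, reads in full: "Elephant treatment will be interacted with concordant doctor". It names no reference group.

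**The concern.** Up to the end of the Video 1 questions, a respondent in the CDC column (cells 2 and 6) has had the same experience as one in the baseline column (cells 1 and 5): a partner doctor, concordant or discordant, giving the no-elephant script. The columns separate only at Video 2. For anything recorded before that, the four cells form one randomised no-elephant group, and main test 3 uses part of it.

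What is at stake is precision on the ratings taken straight after the elephant message. It matters more for Hispanic respondents, who are analysed separately with half the sample of Black respondents, and it could matter for the interaction with concordance, since section 1 predicts that acknowledgement helps discordant doctors most.

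**Working it through.** The plan gives no power calculation, effect size, SD or alpha, so it has no figure of that kind to reproduce. Its counts agree: "There are 8 content-variants for each video, shown here", each concordant or discordant, gives 8 × 2 = 16, as in "sample within each of 16 treatment cells" (section 5.3); and 10,000 + 5,000 = 15,000 (section 2.2).

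**Which cells qualify.** Figure 1 has four columns of four cells: baseline (1c/d, 5c/d), CDC (2c/d, 6c/d), and two elephant columns (3 and 7; 4 and 8). Before Video 2 the no-elephant cells are 1, 2, 5 and 6, each c/d, which is 8 of 16. Test 3 uses 4 of those 8. One point needs reconciling separately: secondary test 6 interacts the CDC and elephant treatments, but Figure 1 has no cell combining them.

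**Which outcomes qualify.** Video 1 ratings do, and so does Video 1 viewing time if time is logged per video (assumed). Symptom knowledge and health-care trust relate to Video 1 but appear to be endline measures, so they do not qualify. Nor does a family 1 index over all three videos.

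**Standard error.** Assume n respondents in every column, SD 1, and no adjustment for doctors.

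- Planned: SE = √(1/n + 1/n) = √(2/n).
- All no-elephant cells: SE = √(1/n + 1/(2n)) = √(1.5/n).
- Ratio: √0.75 = 0.866, so the SE is 13.4% smaller. The variance falls by 25%, equivalent to 1/0.75 = 1.33 times the respondents in this contrast.

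With equal allocation over 17 arms (16 cells plus control; assumed):

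| Group | n per column | SE planned | SE extended |
|---|---|---|---|
| Black | 4 × 10,000/17 = 2,353 | 0.0292 | 0.0252 |
| Hispanic | 4 × 5,000/17 = 1,176 | 0.0412 | 0.0357 |

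**Power (two-sided 5%, no multiplicity adjustment; assumed).** An effect detected with 80% power by the planned contrast would be detected with 89.9%. The control share is not stated. As it goes from 0 to 1/3, the effect detectable with 80% power changes as follows:

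- Black: 0.079 to 0.069 SD with no control; 0.097 to 0.084 SD with one third in control.
- Hispanic: 0.112 to 0.097 SD with no control; 0.137 to 0.119 SD with one third in control.

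**Unequal allocation.** If the CDC column is r times the baseline column, and the elephant column equals the baseline column, the SE ratio is √[(1 + 1/(1 + r))/2]. For r = 0.5 it is 0.913 (8.7% smaller); for r = 2 it is 0.816 (18.4% smaller).

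**Doctor-video random effect.** Section 5.3 also plans standard errors that allow for this effect. Cells 2 and 6 add respondents but no new Video 1 recordings. As an illustration only, assume m = 10 recordings per script and a doctor-by-script SD of σ, with n = 2,353. The variance is 2/n + 2σ²/m as planned and 1.5/n + 2σ²/m as extended.

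- σ = 0.05: 0.00135 against 0.00114; the SE is 8.2% smaller.
- σ = 0.10: 0.00285 against 0.00264; the SE is 3.8% smaller.

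**Interaction with concordance, if secondary test 3 takes the same reference as main test 3.** SE goes from √(8/n) to √(6/n): 0.0583 to 0.0505 (Black) and 0.0825 to 0.0714 (Hispanic), again 13.4%.

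**The case against.** The planned contrast is randomised, unbiased and prespecified, and a single reference keeps the three limbs of test 3 comparable across outcomes. The plan names no separate Video 1 endpoint, and if family 1 is analysed only as an index over all three videos, cells 1 and 5 are the right reference. All of this stands. It makes the point an efficiency gain for a subset of outcomes.

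Selection is the more serious objection. The exclusions for low quality, speed and incompleteness (sections 4.2 and 6.2) can arise after Video 2. Hypothesis 5 in section 3 anticipates that the CDC video may make people stop paying attention, and that video is in English even for those who chose Spanish. Among retained respondents, cells 2 and 6 could therefore differ from cells 1 and 5. This also stands, and it means the wider reference is clean only in everyone who rated Video 1.

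A reader might infer more than the documents support:

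- *That test 3 is biased.* Its comparison is between randomised cells.
- *That the CDC cells are thrown away.* They are their own limb of test 3 and enter tests 2 and 4. They are missing only from the elephant scripts' reference.
- *That secondary test 3 carries the same restriction.* It states no reference group.
- *That the gain is a fixed 13.4%.* That rests on unstated equal allocation and on unadjusted standard errors.

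**Conclusion.** The point holds for outcomes recorded before Video 2 and analysed on their own. For these, test 3 uses 4 of the 8 valid no-elephant cells. By respondents that is half only under equal allocation; the omitted share is 33% to 67% over the range of r above. The cost is precision alone, and the size of the loss depends on the allocation and the error model. It does not reach endline outcomes or an index that includes later videos. Detectable effects are already small under the planned contrast, so severity is low.

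**What to change.** Add to section 5.3, main item 3:

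> For outcomes recorded before Video 2, the reference for the elephant contrasts is all no-elephant cells (1, 2, 5 and 6), analysed in everyone who rated Video 1, with quality exclusions based only on information recorded up to that point. For endline outcomes and any index combining later videos, the reference stays cells 1 and 5.

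State that secondary item 3 uses the same references. The CDC limb of test 3 on Video 1 ratings can serve as a check in this set, since its true effect there is zero by design.

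No new data are needed. The cost is a second analysis set, which departs from the exclusions in section 4.2, and a reference group that depends on the outcome. Both should be stated in the plan, and the change should be fixed before results are seen.
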